7.5.3 Determining Effect of Copanlisib on CD8 T cell function

CD8+ T cells are expected to not only increased in number in copanlisib-treated tumors but to also be more functional, as measured by cytokine production and decreased expression of inhibitory ligands. CD8+ T cells will be enriched by magnetic separation from disaggregated tumor samples and stimulated *ex vivo*. Production of cytokines IFN γ and TNF α will be measured by flow cytometry. Inhibitory ligands commonly expressed on exhausted T cells including PD-1, Tim3, Lag3, and 2B4 will be measured by flow cytometry as described above.

7.5.4 Determining Effect of Copanlisib on Peripheral Blood Immune Subsets

Peripheral blood mononuclear cells will be isolated from blood samples following removal of the plasma layer. This will be accomplished via standard methods using density gradient

centrifugation with ficoll-paque plus²⁹. Following isolation PBMCs will be resuspended in PBS, counted via trypan blue exclusion and aliquoted into tubes for phenotypic and functional analysis via flow cytometry staining per standard techniques. Markers and cell populations analyzed will be the same as indicated in **Table 9**.

7.5.5 Determining Effect of Copanlisib on Peripheral Blood Cytokines

Cytokine levels from peripheral blood including but not limited to IFN γ , TNF α , TGF β , IL-10, CXCL9, CCL2, IL-6, IL-12, IL-2 and IL-17 will be measured by standard luminex assays from patient plasma.

7.6 Investigator Responsibilities for Translational Research

that we will have approximately 40 paired biopsies (75% success rate based on previous studies) as well as ~6-12 time points for blood draws to assess changes in circulating immune parameters. We estimate 20% of patients would allow a progression biopsy.

8. STUDY SCHEDULE

8.1 Study Calendar – Phase I

Procedure	Baseline ¹ (-28 to 0)	Treatment (1 cycle = 28 days)						EOT ²¹ 30 days (+/-4 days) after last study drug	Survival Follow-Up ²² Q12 weeks (± 2 weeks)
		Cycle 1			Cycle 2 and higher				
		D1 (±3 days)	D8 (+1 day)	D15 (+3 days)	D1 (±3 days)	D8 (+1 day)	D15 (+3 days)		
Administrative Procedures									
Informed Consent	X								
Inclusion/Exclusion Criteria	X								
Demographics and Med Hx ²	X								
Copanlisib		X	X	X	X	X	X		
Nivolumab		X			X				
Post-study anticancer therapy and survival status									X
Clinical Assessments									
Physical Examination, ECOG ³	X	X	X	X	X		X	X	
Vital Signs ⁴	X	X	X	X	X	X	X	X	
Blood Pressure (infusion days) ⁵		X	X	X	X	X	X		
Weight	X	X			X			X	
Height (may be from prior visit)	X								
Review Adverse Events		X	X	X	X	X	X	X	
Con Med Review	X	X	X	X	X	X	X	X	
Laboratory Assessments									
CBC with Differential ^{6, 16}	X	X	X	X	X	X	X	X	
Chemistry Panel ^{7, 16}	X	X	X	X	X	X	X	X	
Glucose ⁸		X	X	X	X	X	X		
Hemoglobin A1C ¹⁶	X				X ⁹			X	
Lipid Panel ^{10, 16}	X	X	X	X	X(even cycles)			X	
TSH ^{11, 16}	X	X		X	X		X	X	
PT, INR and aPTT ¹⁶	X								
HBsAg, HCV Ab, HIV ¹²	X								
CMV PCR ^{13, 16}	X				X				
Pregnancy Test ^{14, 16}	X	X			X			X	
Urinalysis ^{15, 16}	X				X(even cycles)				
Urine protein:creatinine ratio (UPCR)	X								
12-lead ECG	X							X	
MUGA or echocardiogram ¹⁷	X							X	
CEA	X	X			X			X	
Efficacy Assessments									
Tumor Imaging ¹⁸	X				X(odd cycles)			X	
Tissue and Blood for Correlative Studies									
Fresh Tumor Biopsy ¹⁹	X						X	X	
Archival Tumor Sample	X								
Blood for PBMC (180cc) ^{20, 16}		X		X	X(odd cycles)			X	

Procedure	Baseline ¹ (-28 to 0)	Treatment (1 cycle = 28 days)						EOT ²¹ 30 days (+/-4 days) after last study drug	Survival Follow-Up ²² Q12 weeks (± 2 weeks)
		Cycle 1			Cycle 2 and higher				
		D1 (±3 days)	D8 (+1 day)	D15 (+3 days)	D1 (±3 days)	D8 (+1 day)	D15 (+3 days)		
Blood for plasma (20 cc) ^{20, 16}		X		X	X(odd cycles)			X	

In order to minimize the need for research-only in-person visits, telemedicine visits may be substituted for in-person clinical trial visits or portions of clinical trial visits where determined to be appropriate and where determined by the investigator not to increase the participants risks. Prior to initiating telemedicine for study visits the study team will explain to the participant, what a telemedicine visit entails and confirm that the study participant is in agreement and able to proceed with this method. In the event telemedicine is not deemed feasible, the study visit will proceed as an in-person visit. Telemedicine visits will be conducted using HIPAA compliant method approved by the Health System and within licensing restrictions.

1. Baseline evaluations should occur within 28 days prior to registration, unless otherwise noted. No window applies to demographics, consent, or height at baseline.
2. Includes history of lung disease, cardiovascular disease, diabetes, HIV, hepatitis B or C infection, and complete cancer history, including primary site of cancer, gross location of primary tumor, histology, histologic grade, date of initial diagnosis, date of metastatic diagnosis, prior cancer therapy regimens
3. A complete physical exam will be performed at baseline; focused physical exams will be done thereafter. Physical exams and AE assessments can be done up to 3 days prior to dosing.
4. Temperature, pulse, blood pressure, respiratory rate, and pulse oxygen will be collected at baseline, and prior to each dose of study drug, and at EOT visit.
5. Blood pressure will be measured every 5-10 minutes prior to each copanlisib dose (no more than 4 measurements) until there are 2 consecutive results $\leq 150/90$ mmHg. If the blood pressure is $\geq 150/90$ mmHg, the investigator can consider a medical intervention e.g. administration of dihydropyridine calcium channel blocker), or delaying the infusion of the study drug. Blood pressure will be measured at pre-dose, 30 min (mid-infusion), 60 min (end of infusion), and 1h and 2h after the end of copanlisib infusion (± 15 minute window for all BP measurements).
6. CBC with differential includes: absolute neutrophil count, absolute lymphocyte count, absolute eosinophil count, and platelet count
7. Chemistry panel includes: albumin, alkaline phosphatase, total bilirubin (direct bilirubin if total bili is $> ULN$), bicarbonate, BUN, calcium, chloride, creatinine, glucose, potassium, total protein, SGOT [AST], SGPT [ALT], sodium, LDH, magnesium, phosphorus, uric acid. Amylase and lipase to be down at screening and Day1 of every cycle.
8. **Fasting** glucose will be measured at 0h (pre-dose), and 1 hour (+/- 15 min) after completion of copanlisib infusion and subsequently if clinically indicated at the discretion of the investigator. NOTE: if patient needs to take a low glycemic meal on infusion days, then glucose test should be taken prior to meal intake. Glucose measurements may be done by laboratory analysis or in capillary blood.
9. HbA1c to be tested at screening, on Day 1 of every three cycles (4, 7, 10, etc) starting at cycle 4, and at the EOT visit
10. HDL, LDL, triglycerides, total cholesterol; performed at Screen, Cycle 1 Day 1, Day 8, and Day 15; then Day 1 of every other cycle (starting at Cycle 2)

11. If TSH is abnormal, T3 and FT4 will be assessed.
12. Patients with positive tests for HBsAg or HIV are excluded from study. Patients with positive test for anti-HCV antibody will be eligible if they are negative for HCV-RNA. These patients should perform HCV RNA test with PCR monthly through treatment and 6 months thereafter. If viral load becomes positive, patient should be withdrawn from the study.
13. CMV PCR may be done up to 7 days prior to each Day 1 visit. CMV PCR should be done with every cycle through cycle 6, then every 3 cycles thereafter.
14. Serum or urine pregnancy test required for WOCBP only. If urine pregnancy results cannot be confirmed as negative, a serum pregnancy test is required
15. Bilirubin, hemoglobin, glucose, ketones, leukocytes, nitrite, pH, color, protein, RBC and WBC count, and specific gravity. Performed at baseline and Day 1 of every other cycle (starting at cycle2).
16. Labs and research blood should be collected within a window of 3 days prior to dosing. Labs may be repeated prior to dosing if needed.
17. MUGA scan or echocardiogram to measure LVEF; the method chosen at baseline must be the same throughout the whole study period (baseline and EOT); at EOT visit must be done if not previously done within 4 weeks
18. Radiologic evaluations and tumor measurements will be performed at baseline (within 28 days of dosing), prior to each odd cycle (up to 1 week prior), and at End of Treatment visit. If patient comes off study for reasons other than disease progression, subject may have additional radiologic evaluations every 8 weeks until progression or start of new anti-cancer therapy. CT of the chest/abdomen/pelvis with contrast will be used, however, non-contrast CT chest and MRI abdomen/pelvis will be done for patients with contrast allergies.
19. Biopsy to be collected at baseline and 6 weeks after first dose of study drug (\pm 3 days, but before Cycle 2 Day 15 study drug administration). An optional biopsy may be performed at the time of progression. Approximately 6 core biopsy specimens will be obtained at each biopsy.
20. Blood for PBMC and plasma will be collected at baseline/prior to first dose, 2 weeks after first dose, on Day 1 of each odd cycle, and at progression or EOT visit.
21. EOT Clinical assessments do not need to be repeated if they were done within last 7 days. Hemoglobin A1C, 12-lead ECG, and MUGA or echocardiogram do not need to be repeated if they were done within the last 4 weeks.
22. Subjects who discontinue treatment will be followed (by phone, email or visit) every 12 weeks (\pm 2 weeks) after completion of EOT visit for up to 2 years or study closure to monitor overall survival. Information on other cancer therapies and disease status will also be collected. In addition, SAEs that occur within 100 days (+14 day reporting window) of the end of treatment or before initiation of a new antineoplastic treatment should also be followed and recorded.

8.2 Study Calendar – Phase II

Procedure	Screen ¹ D -28 to 0	Treatment (1 cycle = 28 days)						EOT ²¹ 30 days (+/-4 days) after last study drug	Survival Follow-Up ²² Q12 weeks (± 2 weeks)
		Cycle 1			Cycle 2 and higher				
		D1 (±3 days)	D8 (+1 day)	D15 (+3 days)	D1 (±3 days)	D8 (±1 day)	D15 (-1/+3 days)		
Administrative Procedures									
Informed Consent	X								
Inclusion/Exclusion Criteria	X								
Demographics and Med Hx ²	X								
Copanlisib		X	X	X	X	X	X		
Nivolumab		X			X				
Post-study anticancer therapy and survival status									X
Clinical Assessments									
Physical Examination, ECOG ³	X	X		X	X		X	X	
Vital Signs ⁴	X	X	X	X	X	X	X	X	
Blood Pressure (infusion days) ⁵		X	X	X	X	X	X		
Weight	X	X			X			X	
Height	X								
Review Adverse Events		X	X	X	X	X	X	X	
Con Med Review	X	X	X	X	X	X	X	X	
Laboratory Assessments									
CBC with Differential ^{6, 16}	X	X	X	X	X	X	X	X	
Chemistry Panel ^{7, 16}	X	X	X	X	X	X	X	X	
Glucose ⁸		X	X	X	X	X	X		
Hemoglobin A1C ¹⁶	X				X ⁹			X	
Lipid Panel ^{10, 16}	X				X(even cycles)			X	
TSH ^{11, 16}	X	X		X	X		X	X	
PT, INR and aPTT ¹⁶	X								
HBsAg, HCV Ab, HIV ¹²	X								
CMV PCR ^{13,16}	X				X				
Pregnancy Test ^{14, 16}	X	X			X			X	
Urinalysis ^{15, 16}	X				X(even cycles)				
Urine protein:creatinine ration (UPCR)	X								
12-lead ECG	X							X	
MUGA or echocardiogram ¹⁷	X							X	
CEA	X	X			X			X	
Efficacy Assessments									
Tumor Imaging ¹⁸	X				X(odd cycles)			X	
Tissue and Blood for Correlative Studies									
Fresh Tumor Biopsy ¹⁹	X						X	X	
Archival Tumor Sample	X								
Blood for PBMC (100cc) ^{20, 16}		X		X	X(odd cycles)			X	
Blood for plasma (20 cc) ^{20, 16}		X		X	X(odd cycles)			X	

In order to minimize the need for research-only in-person visits, telemedicine visits may be substituted for in-person clinical trial visits or portions of clinical trial visits where determined to be appropriate and where determined by the investigator not to increase the participants risks. Prior to initiating telemedicine for study visits the study team will explain to the participant, what a telemedicine visit entails and confirm that the study participant is in agreement and able to proceed with this method. In the event telemedicine is not deemed feasible, the study visit will proceed as an in-person visit. Telemedicine visits will be conducted using HIPAA compliant method approved by the Health System and within licensing restrictions.

1. Baseline evaluations should occur within 28 days prior to registration, unless otherwise noted. No window applies to demographics, consent, or height at baseline.
2. Includes history of lung disease, cardiovascular disease, diabetes, HIV, hepatitis B or C infection, and complete cancer history, including primary site of cancer, gross location of primary tumor, histology, histologic grade, date of initial diagnosis, date of metastatic diagnosis, prior cancer therapy regimens
3. A complete physical exam will be performed at baseline; focused physical exams will be done thereafter. Physical exams and AE assessments can be done up to 3 days prior to dosing.
4. Temperature, pulse, blood pressure, and respiratory rate, and pulse oxygen will be collected at baseline, and prior to each dose of study drug, and at EOT visit.
5. Blood pressure will be measured every 5-10 minutes prior to each copanlisib dose (no more than 4 measurements) until there are 2 consecutive results $\leq 150/90$ mmHg. If the blood pressure is $\geq 150/90$ mmHg, the investigator can consider a medical intervention (e.g. administration of dihydropyridine calcium channel blocker), or delaying the infusion of the study drug. Blood pressure will be measured at 0h (pre-dose), 30 min (mid-infusion), 60 min (end of infusion), and 1h and 2h after the end of copanlisib infusion (± 15 minute window for all BP measurements).
6. CBC with differential includes: absolute neutrophil count, absolute lymphocyte count, absolute eosinophil count, and platelet count
7. Chemistry panel includes: albumin, alkaline phosphatase, total bilirubin (direct bilirubin if total bili is $> \text{ULN}$), bicarbonate, BUN, calcium, chloride, creatinine, glucose, potassium, total protein, SGOT [AST], SGPT [ALT], sodium, LDH, magnesium, phosphorus, uric acid. Amylase and lipase to be down at screening and Day1 of every cycle.
8. **Fasting** glucose will be measured at 0h (pre-dose), and 1 hour (± 15 min) after completion of copanlisib infusion and subsequently if clinically indicated at the discretion of the investigator. NOTE: if patient needs to take a low glycemic meal on infusion days, then glucose test should be taken prior to meal intake. Glucose measurements may be done by laboratory analysis or in capillary blood.
9. HbA1c to be tested at screening, on Day 1 of every three cycles (4, 7, 10, etc) starting at cycle 4, and at the EOT visit.
10. HDL, LDL, triglycerides, total cholesterol; performed at Screen and Day 1 of every other cycle (starting at Cycle 2)
11. If TSH is abnormal, T3 and FT4 will be assessed.
12. Patients with positive tests for HBsAg or HIV are excluded from study. Patients with positive test for anti-HCV antibody will be eligible if they are negative for HCV-RNA. These patients should perform HCV RNA test with PCR monthly through treatment and 6 months thereafter. If viral load becomes positive, patient should be withdrawn from the study.
13. CMV PCR may be done up to 7 days prior to each Day 1 visit. CMV PCR should be done with

every cycle through cycle 6, then every 3 cycles thereafter.

14. Serum or urine pregnancy test required for WOCBP only. If urine pregnancy results cannot be confirmed as negative, a serum pregnancy test is required.
15. Bilirubin, hemoglobin, glucose, ketones, leukocytes, nitrite, pH, color, protein, RBC and WBC count, and specific gravity. Performed at baseline and Day 1 of every other cycle (starting at cycle2).
16. Labs and research blood should be collected within a window of 3 days prior to dosing. Labs may be repeated prior to dosing if needed.
17. MUGA scan or echocardiogram to measure LVEF; the method chosen at baseline must be the same throughout the whole study period (baseline and EOT); at EOT visit must be done if not previously done within 4 weeks.
18. Radiologic evaluations and tumor measurements will be performed at baseline (within 28 days of dosing), prior to each odd cycle (up to 1 week prior), and at End of Treatment visit. If patient comes off study for reasons other than disease progression, subject may have additional radiologic evaluations every 8 weeks until progression or start of new anti-cancer therapy. CT of the chest/abdomen/pelvis with contrast will be used, however, non-contrast CT chest and MRI abdomen/pelvis will be done for patients with contrast allergies.
19. Biopsy to be collected at baseline and 6 weeks after first dose of study drug (\pm 3 days, but before Cycle 2 Day 15 study drug). An optional biopsy may be performed at the time of progression. Approximately 6 core biopsy specimens will be obtained at each biopsy. Tumor biopsy will not be performed if the tumor is not accessible or if biopsy is considered not in the patient's best interest.
20. Blood for PBMC and plasma will be collected at baseline/prior to first dose, 2 weeks after first dose, on Day 1 of each odd cycle, and at progression or EOT visit.
21. EOT Clinical assessments do not need to be repeated if they were done within last 7 days. Hemoglobin A1C, 12-lead ECG, and MUGA or echocardiogram do not need to be repeated if they were done within the last 4 weeks.
22. Subjects who discontinue treatment will be followed (by phone, email or visit) every 12 weeks (\pm 2 weeks) after completion of EOT visit for up to 2 years or study closure to monitor overall survival. Information on other cancer therapies and disease status will also be collected. In addition, SAEs that occur within 100 days (+14 day reporting window) of the end of treatment or before initiation of a new antineoplastic treatment should also be followed and recorded.

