1.5 Study Design

This is a multi-center, open-label, Phase I/II study. Phase 1 consists of a 3+3 dose de-escalation design to determine the dose of copanlisib for use in combination with nivolumab. Approximately 6-18 subjects with solid tumors will be treated in Phase I and will be monitored for dose limiting toxicities (DLTs) through their first cycle of treatment. Complete information on the definition of DLTs and dose de-escalation rules can be found in **Section 4.3**.

The Phase II portion of the study will evaluate the safety and clinical activity of copanlisib and nivolumab in two cohorts of patients with previously treated metastatic colon cancer. Cohort A will enroll patients with PI3K mutation and Cohort B will enroll patients with wildtype PI3K status. Twenty-one patients are targeted for enrollment in each cohort, for an approximate total of 42 patients in Phase II. Enrollment in Phase II will be initiated once the recommended phase II dose (RP2D) has been determined in Phase I.

For all patients, the study will consist of a screening period, a treatment period, and a follow-up period. Screening evaluations will be done within 28 days prior to the start of study treatment.

Each treatment cycle is 28 days. Patients in both Phase I and Phase II will receive nivolumab on Day 1 of each cycle (every 4 weeks) and copanlisib on either Day 1, Day 8, and Day 15 of each cycle (3 week on, one week off) or on Day 1 and 15 of each cycle (every 2 weeks), depending on the dose level and RP2D. Complete information on study drug administration, schedule, and dosing can be found in **Section 4.2**.

Phase II enrollment will be carried out in 2 stages so that the study can terminate early if the combination of copanlisib and nivolumab is not sufficiently effective. In the first stage, 12 subjects will be accrued to each cohort. If there are no responders among the first 12 patients, the study will be terminated for futility. Otherwise, 9 additional patients will be accrued for a total of 21 treated subjects. If ≥ 3 out of the 21 patients have a response, then the trial will be considered a success for that cohort.

Clinical and immune responses will be evaluated at baseline and during treatment through tumor assessments, biopsies, and PBMC and plasma collection. Tumor assessments will be made using RECIST 1.1.

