4.4 Dose Modification and Toxicity Management

4.4.1 Dosing Delays and Modifications

Study treatments are scheduled on a 3 weeks on, 1 week off schedule.

- Start of a treatment cycle (Day 1) will be delayed for toxicity until retreatment criteria are met. The Principal Investigator must approve retreatment if delays last longer than 1 week. If delays are required due to toxicity related to one study drug but not the other, all study treatment will be delayed.
- If the day 8 or day 15 dose of copanlisib needs to be delayed longer than 2 days due to toxicity, the dose(s) should be skipped and the remainder of the cycle continued once retreatment criteria are met. The intention here is to keep the length of each cycle to 4 weeks, when possible. Skipped doses will be documented in the study database.

There will be no dose reductions to nivolumab. Dose reductions to copanlisib will use the dose levels outlined in **Table 1** and dose reduction criteria outlined in **Table 4**. If a patient is already receiving the lowest dose level of copanlisib and meets criteria for further decrease, study treatment will be discontinued permanently. There will be no dose re-escalation for DLTs. Dose re-escalation may be allowed for non-DLTs at the PI's discretion after patient has fully recovered from the toxicity and in the absence of any other

adverse events that require dose-reduction, with the exception of non-infectious pneumonitis.

Dosing of study therapy will be delayed for the following criteria (or **Table 4** criteria):

- AST/ALT $>3 \times$ ULN
- Total bilirubin $> 1.5 \times$ ULN ($> 2.0 \times$ ULN for subjects with Gilbert's syndrome)
- Creatinine $> 1.5 \times$ ULN or GFR < 40 mL/min/1.73 m²
- Hemoglobin < 8 g/dL
- ANC < 1250 /uL (day 1) and < 1000 (days 8 and 15) – hold both study drugs
- Platelets $< 75 \times 10^3$ /uL
- Fasting Glucose (Cycle 1 Day 1) >125 mg/dL (non-diabetic patients) or ≥ 160 mg/dL (diabetic patients)
- Fasting glucose (all other days) > 160 mg/dL
- CMV PCR > 500 IU/mL (tested each cycle for cycles 1-6, and every 3 months thereafter)
- Any Grade ≥ 2 non-skin, nivolumab-related adverse event, with the following exceptions:
 - Grade 2 fatigue
 - Grade 2 lab abnormalities
 - Grade 2 hypothyroidism or thyroiditis
- Any Grade ≥ 3 skin nivolumab-related AE
- Any Grade ≥ 3 nivolumab-related laboratory abnormality with the following exceptions:
 - Grade 3 lymphopenia

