Drug-related AEs	Grade (CTCAE v5.0) or measurement	Action taken to study drugs	Retreatment Dose Level	AE management	Monitor and follow-up
	Grade ≥ 3	Withhold	Decrease by one dose level at the PI's discretion	
 • Treatment with transfusion or growth factors allowed at PI's discretion 	
Other non-hematological toxicities	Grade 3	Withhold	1 st : no dose change 2 nd -3 rd : decrease by one dose level 4 th : discontinue		
	Grade 4 or any toxicity requiring delay for >21 days	Permanently discontinue	N/A		

 1. Persistent occurrence is defined as repeated post-infusion blood glucose measurements taken at different times during the cycle despite optimal glucose-lowering therapy in consultation with endocrinologist 2. Infusion may proceed/resume on scheduled day if BP recovers to <150/90 mmHg for 2 consecutive measurements and symptoms (if present) resolve. 3. Despite maximum supportive therapy 4. Thrombocytopenia, neutropenia, febrile neutropenia, anemia, INR or PTT with bleeding 
General instructions:
 
 • For situations where drug is withheld due to a copanlisib-related AE, treatment can be resumed after AE has been reduced to Grade 1 or 0 unless otherwise indicated. Treatment should be permanently discontinued if AE does not resolve within 12 weeks of last dose. • If patient is already on lowest dose level and meets criteria for further decrease, study drug will be discontinued permanently. • Dose re-escalation may be allowed at the PI's discretion after patient has fully recovered from the toxicity and in the absence of any other adverse events that require dose-reduction, with the exception of non-infectious pneumonitis. • Abbreviations: SGLT2 = Sodium/Glucose co-transporter 2; DPP4 = Dipeptidyl peptidase 4; PJP= pneumocystis jiroveci pneumonia 					

In order to standardize the management of AEs for all subjects, treatment management algorithms are included in **Appendix C**. Additional AE treatment management algorithms included in the nivolumab IB might be considered for individual cases.

Subjects who require a delay in study treatment should be re-evaluated weekly or more frequently if clinically indicated and resume dosing when re-treatment criteria are met.

Subjects may resume treatment with study drug when the nivolumab-related AE(s) resolve to grade ≤ 1 or baseline value, with the following exceptions:

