- Subjects may resume treatment in the presence of grade 2 fatigue.
- Subjects who have not experienced a Grade 3 drug-related skin AE may resume treatment in the presence of Grade 2 skin adverse event
- Treatment-related pulmonary toxicity, diarrhea, or colitis must have resolved to baseline before treatment is resumed.
- Treatment-related endocrinopathies adequately controlled with only physiologic hormone replacement may resume treatment, which include grade 2 hyperglycemia, hypothyroidism and thyroiditis.

Subjects should be permanently discontinued if AE does not resolve within 12 weeks of last dose or corticosteroids cannot be reduced to ≤ 10 mg prednisone or equivalent per day within 12 weeks.

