9.2 Methods for Evaluation of Measurable Disease

Imaging should include the chest, abdomen, and pelvis. Tumor imaging is strongly preferred to be acquired by computed tomography (CT). For the abdomen and pelvis, contrast-enhanced magnetic resonance imaging (MRI) may be used when CT with iodinated contrast is contraindicated, or when local practice mandates it. The same imaging technique regarding modality, ideally the same scanner, and the use of contrast should be used in a participant throughout the study to optimize the reproducibility of the assessment of existing and new tumor burden and improve the accuracy of the assessment of response or progression based on imaging. Body scans should be performed with breath-hold scanning techniques, if possible.

All baseline evaluations should be performed as closely as possible to the beginning of treatment and no more than 28 days before the beginning of the treatment. The site study team must review screening images to confirm the participant has measurable disease per RECIST 1.1. Subjects will be evaluated for anti-tumor effect by follow-up imaging as outlined in the study calendar. All subsequent scans (post-treatment) will be compared to the same pretreatment scan that was used prior to initiating of study treatment.

All measurements should be taken and recorded in metric notation using a ruler or calipers.

The definition of measurability of lesions on CT scan is based on the assumption that CT slice thickness is 5 mm or less. If CT scans have slice thickness greater than 5 mm, the minimum size for a measurable lesion should be twice the slice thickness.

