11.2 Statistical Analyses

Data will be summarized descriptively within each phase overall and by subgroups of interest (e.g. cohort). The descriptive summary including demographics and baseline variables will include counts and percentages for categorical variables and means, medians, standard deviations, and quartiles for continuous variables.

ORR at 6 months, the primary outcome for Phase II, will be summarized using counts and percentages. Logistic regression will be used to compare the ORR between the two cohorts as well as to identify risk factors associated with ORR. Other binary outcomes (e.g. disease control at 6 months (SD+PR+CR) and immunologic response) will be analyzed using the same methods.

Time to event outcomes include overall survival (OS) and progression free survival (PFS). Overall survival is defined as the time from the first dose until death. Individuals without an event will be censored at the date of last contact. Progression free survival is defined as the time from the first dose until progression or death. Individuals who die will be counted as having progressed. Individuals without an event will be censored at the date of the last evaluation for progression. Kaplan-Meier curves will be used to graphically summarize the survival function and to estimate the median time to event and the proportion event-free at key intervals (e.g. 6 months) along with 95% confidence intervals. Cox proportional hazards models will be used to compare Cohorts A and B and to identify risk factors associated with OS and PFS. Graphical techniques (e.g. log-log plots) and formal statistical testing (e.g. Schoenfeld tests) will be used to assess the proportional hazards assumption. If necessary, alternate models (e.g. incorporating a time variable) will be considered.

Safety will be monitored continuously throughout the study, including the phase II component. Weekly team meetings and a minimum of monthly investigator calls will be conducted to review ongoing and resolved toxicity.

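### Scans follow odd cycles while 6-month ORR, 6-month DCR and PFS follow the calendar, so Day 1 delays date progression late and, beyond about 2 weeks in total, can push the Cycle 7 scan past 6 months

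*Combined protocol and SAP*

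**What the plan says.** Footnote 18 is worded the same way in both study calendars (sections 8.1 and 8.2). After baseline, imaging is due "prior to each odd cycle (up to 1 week prior), and at End of Treatment visit", and the Tumor Imaging row marks odd cycles only. Section 9.2 sets no schedule of its own: "Subjects will be evaluated for anti-tumor effect by follow-up imaging as outlined in the study calendar".

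Section 1.5 states "Each treatment cycle is 28 days", so Cycles 3, 5 and 7 nominally start at weeks 8, 16 and 24. Section 4.4.1 then lets the cycle start move: "Start of a treatment cycle (Day 1) will be delayed for toxicity until retreatment criteria are met". Day 8 and Day 15 doses are treated differently. If they slip by more than 2 days they are skipped, and the section explains: "The intention here is to keep the length of each cycle to 4 weeks, when possible".

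The endpoints use a different clock. Section 11.2 says "ORR at 6 months, the primary outcome for Phase II, will be summarized using counts and percentages". It also takes disease control at 6 months and measures PFS from first dose. No section defines a 6-month assessment window, a rule for a late scan, or a method for interval-censored progression.

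**The concern.** Scan dates depend on toxicity, but the endpoints do not. A patient whose cycles start late is scanned later and less often, so progression is dated later for a reason unrelated to the tumour. That patient may also have two on-treatment scans, not three, before the 6-month cut for the primary endpoint.

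The protocol expects delays long enough to matter:

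- Section 4.4.1 lists many laboratory and adverse-event triggers and requires approval of retreatment when a delay exceeds 1 week.
- Section 4.4.5 asks for steroid treatment to finish at least 14 days before study treatment resumes.
- Section 2.1 puts hyperglycemia among the most common single-agent copanlisib events (over 20% of patients) and grade 4 neutropenia at 12%.

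The success rule is 3 or more responders out of 21 per cohort, so one uncounted response can change a cohort's result.

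**Working it through.** **Inputs.** Cycle length is 28 days (section 1.5). Scans fall at Cycles 3, 5 and 7, up to 7 days early (footnote 18). The design has 12 then 9 patients per cohort, stops at 0 of 12, succeeds at 3 or more of 21, and tests ORR 5% against 20% (section 11.1). Six months is taken as 365.25/2 = 182.6 days. Delay rates and PFS medians are assumptions, because the documents give none.

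**1. The plan's own figures.** P(success) = sum over x = 1 to 12 of Bin(x; 12, p) × P(Bin(9, p) ≥ 3 − x). At p = 0.20 this is 0.803 and at p = 0.05 it is 0.080. Both match the stated 0.80 and 0.08.

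**2. Scan dates.** With cumulative Day 1 delay d, the Cycle 7 scan falls on days 161 + d to 168 + d.

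| d (days) | Cycle 7 scan (day) | By day 182.6? |
|---|---|---|
| 0 | 161-168 | yes |
| 14 | 175-182 | yes |
| 21 | 182-189 | only if taken early |
| 28 | 189-196 | no |

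Slack is 182.6 − 168 = 14.6 days, or 182.6 − 161 = 21.6 days if the scan is a week early. Appendix E calls for confirmation at 4 weeks or more. A response first seen at Cycle 5 is therefore normally confirmed at Cycle 7, with the same slack.

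**3. How often the Cycle 7 scan is late (assumed rates).** There are six cycle starts (Cycles 2 to 7), each delayed independently with probability p, and the scan is taken on Day 1. It is late after at least three 7-day delays, two 14-day delays or one 21-day delay.

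| p | 7 days | 14 days | 21 days |
|---|---|---|---|
| 5% | 0.2% | 3% | 27% |
| 10% | 2% | 11% | 47% |
| 20% | 10% | 34% | 74% |
| 30% | 26% | 58% | 88% |

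These figures apply to patients who remain on treatment to Cycle 7.

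**4. Missed responders (assumed share m).** Replace p by p(1 − m) in step 1.

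| m | Power | Type I error |
|---|---|---|
| 0 | 0.803 | 0.080 |
| 5% | 0.772 | 0.071 |
| 10% | 0.737 | 0.063 |
| 20% | 0.656 | 0.047 |

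Requiring 4 responders in place of 3 gives power 0.624, so 0.803 − 0.624 = 0.179 of the power comes from exactly 3 responders.

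**5. PFS (simulated, assumed).** True PFS is exponential with median 60-180 days, 15-30% of cycles are delayed by 14-21 days, and progression is dated at the next odd-cycle scan. Compared with no delay, mean observed PFS rises by about 4-11 days and observed 6-month PFS by about 1-6 points. The observed median can move either way because it sits on the scan grid. If only one cohort is delayed and true PFS is equal, the observed hazard ratio is about 0.87-0.97. If neither is delayed it is 1.00.

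**6. One delayed patient type.** A 4-week delay before Cycle 3 gives scans at weeks 12, 20 and 28, so the last scan before 6 months is at week 20, not week 24. With S(t) = 2^(−t/median), medians of 8, 12 and 16 weeks give S(20) = 18%, 32%, 42% against S(24) = 13%, 25%, 35%.

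**The case against.** The case for leaving the schedule alone has real substance.

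- **Not every delay moves a scan.** Day 8 and Day 15 slippage is absorbed by skipping the dose. A scan already taken in the week before Day 1 stays where it is, and only later scans move. Total delay of up to about 2 weeks keeps all three scans inside 6 months. A reader might infer that any toxicity delay distorts 6-month ORR and DCR. The documents do not support that.
- **Cohort bias is conditional.** A reader might infer that the A versus B comparison is biased as planned. Section 4.2 gives both cohorts the same regimen, they share one calendar, and nothing suggests that delays differ by PIK3CA status. Equal delays should create no systematic difference.
- **The 18/32/42% figures are not cohort estimates.** They describe only patients with a 4-week delay before Cycle 3. If an assumed 20% of patients had that delay, the rise would be 0.2 × (17.7 − 12.5) = 1.0 point to 0.2 × (31.5 − 25.0) = 1.3 points.
- **Not all progression waits for a scan.** Deaths count on their own date, held patients are re-evaluated at least weekly, and patients who deteriorate before re-imaging are coded as progressing.
- **Very long holds are not settled.** The general limit reads "Treatment should be permanently discontinued if AE does not resolve within 12 weeks of last dose", and a 12-week hold after Cycle 1 Day 15 would put the first scan at about week 17-18. One Table 4 row (other non-hematological toxicities) instead stops treatment after a delay of more than 21 days. The extreme case cannot be taken as the plan's intention.
- **For ORR the error is conservative.** Missed responders lower type I error as well as power.

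All of this narrows the size and reach of the point. It does not give the scans a calendar anchor or define the 6-month assessment.

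**Conclusion.** The concern holds in a limited form. Following the plan as written makes assessment times depend on toxicity while the endpoints run from first dose. Later dating of progression in delayed patients is the best-supported consequence. For 6-month ORR the threat is mainly a cumulative Day 1 delay above about 2 weeks, or 3 if the scan is taken early. It then costs power: about 0.77, 0.74 or 0.66 if 5%, 10% or 20% of responders go uncounted. For DCR the direction is not fixed. Stable disease carried forward from Cycle 5 would inflate it, while treating a missing 6-month scan as failure would lower it, and the plan does not say which applies. The comparison of cohorts is affected only if delays differ between them.

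Every size given here depends on assumed delay rates, and the PFS figures also assume exponential times and scan-detected progression. The stated power and type I error are correct as calculated. This is a weakness in the assessment schedule that is cheap to remove, not an error in the sample size.

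**What to change.** In footnote 18 of both study calendars, replace the odd-cycle anchor with: *every 8 weeks from Cycle 1 Day 1 (weeks 8, 16, 24 and so on; window minus 1 week), regardless of dose delays or skipped doses*. Change the Tumor Imaging row to match. In section 11.2, take the week-24 scan as the 6-month assessment for ORR and DCR.

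The third scan is then due by day 168 for every patient still under assessment, 14 days before 6 months, whatever the dosing delay. The sample size, power (0.803) and type I error (0.080) do not change. There is precedent in the protocol: the on-treatment biopsy is already timed from first dose.

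The cost is a small wording change. Patients without delays need no extra scans. The downside is that a scan may not coincide with a dosing visit when a patient is on hold. The documents do not give accrual to date. If patients have already been followed under Version 7.0 or earlier, the analysis should state which schedule applied to whom.

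The sponsor must also reconcile two pairs of passages: off-treatment imaging every 8 weeks (footnote 18) against every 10 weeks (section 1.5), and the 21-day against the 12-week hold limit in section 4.4.1.
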